2. HIV
3. Planning to go for breast enhancement or gender reassignment surgery in the next 6 months
4. Known history of peanut allergy (because the study drug contains peanut oil)
5. Active deep vein thrombosis, pulmonary embolism or history of these conditions
6. Active arterial thromboembolic disease or history of these conditions
7. Active cardiovascular disorders or history of these conditions (e.g. myocardial infarction, uncontrolled hypertension >150/90 mmHg)
8. Known, suspected, or history of breast cancer
9. Known liver dysfunction or disease
10. Known or history of gallbladder disease. This does not apply to subjects who have undergone cholecystectomy
11. Known or history of hypertriglyceridemia (>400 mg/dl)

**Screening visit:** Informed consent will be obtained. This visit may be conducted during the PI's clinic (if the study volunteer is PI's patient) or at Endocrinology clinical research space at Salus Center. Vital signs (blood pressure, heart rate and weight) will be measured and a general physical examination will be performed.

Subjects who qualify and consent to take part in the study will be assigned a number by a computerized random number generation program and will be randomized (1:1) to receive either progesterone or placebo. An unblinded pharmacist will prepare the study product. Study investigators, staff and the study participants will be blinded.

**Week 0 (baseline):** Subjects will come fasting to the Salus Center. Breast exam and testicular exam will be conducted. They will complete the study questionnaires. Blood sample will be taken for total testosterone, total estradiol, sex hormone binding globulin (SHBG), LH, FSH, complete blood count (CBC), comprehensive metabolic panel (CMP) and research labs. For subjects who are on intramuscular estradiol, this visit will be performed 3-4 days after their last injection. Subjects will be randomized to receive generic micronized progesterone 200 mg or placebo tablets, to be taken at bedtime daily. They will be given a 3-month supply of the study drug. Subjects will be asked to bring the pill bottles back with them at the next visit to assess compliance.

**Week 4:** Subjects will be called by the study coordinator to counsel on drug compliance and to ask for side-effects.

**Week 12:** Subjects will come fasting to the Salus Center. For subjects who are on intramuscular estradiol, this visit will be performed 3-4 days after their last injection. Vital signs (blood pressure, heart rate and weight) will be measured and a general physical examination will be performed. Blood sample will be taken to measure total testosterone, total estradiol, SHBG, LH, FSH and research labs. They will complete the study questionnaires. They will be given a 3-month supply of the study drug. Subjects will be asked to bring the pill bottles back with them at the next visit.

**Week 24 (end of study):** Subjects will come fasting to the Salus Center. For subjects who are on intramuscular estradiol, this visit will be performed 3-4 days after their last injection. Blood sample will be taken to measure CBC, CMP, total testosterone, total estradiol, SHBG, LH, FSH and research labs. Vital signs (blood pressure, heart rate and weight) will be measured and a general physical examination will be performed. Breast exam and testicular exam will be conducted. They will complete the study questionnaires. They will then be discharged from the study.

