**Title: Effect of Progesterone on  
Testosterone concentrations and Breast  
development in Transwomen**

NCT04534881

Date: 9/13/2020

The number of individuals with gender incongruence who present to their physician for hormone therapy has increased manifold in the last decade(1). Testosterone therapy in transgender men (also known as female-to-male transgender or transmen) and estrogen therapy in transgender women (also known as male-to-female transgender or transwomen) respectively is the mainstay of hormone regimen. The proportion of individuals that are transwomen is slightly higher than transmen (60% vs 40%). Transwomen, who are genetically men, receive estradiol replacement with the aim of suppressing serum testosterone and achieving serum estradiol concentrations that mimic the serum concentrations of biological women. This leads to an increase in fat mass, breast growth and decreases in lean mass and masculine pattern hair. However, the results of these changes are often less than satisfactory and additional therapy is required.

Breast development is a major concern for transgender females. There is a great deal of variability among individuals, as evidenced during pubertal development (2). Transgender women do not achieve the same level of breast development as cisgender women do after puberty (3). Typically, transgender women plateau at Tanner stage III and half of the transgender women have a AAA cup size or less (4). In transwomen, breast development is generally maximal at 2 years after initiating hormones (5). However, a more recent study of 229 transgender women participating in the European Network for the Investigation of Gender Incongruence cohort found that breast development reached a plateau within the first 6 months of therapy. Half of the transgender women had a AAA cup size or less and only 10% were size A or more after a year of treatment (4). Not surprisingly, at least 60% of transgender women seek surgical breast augmentation (6).

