**Inclusion criteria**

1. Transwomen, currently on treatment with estradiol therapy for at least 6 months (as their standard of care gender affirming therapy)
2. Has achieved serum estradiol >100 pg/ml at least once, based on clinical labs in past.
3. Age 18-65 years

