### **Study Procedures**

*Clinical laboratory assays:* All measurements will be carried out by Quest diagnostics as part of a standardized contract. We have previously published studies in which measurements of testosterone and estradiol on serum samples of our study subjects were done by Quest Diagnostics (12, 13). Testosterone and estradiol will be measured by current “gold standard” assay: liquid chromatography tandem mass spectrometry. SHBG, FSH and LH concentrations will be measured by a solid-phase, chemiluminescent immunometric assay (Siemens, IMMULITE 2500). Free testosterone and estradiol will be calculated using concentrations of total testosterone, total estradiol, SHBG and albumin by the formula of Sodergard *et al* and Vermuelen *et al* (14, 15).

*Breast size:* The primary measure of breast size will be the difference between breast circumference (measured in centimeters with a tape placed horizontally around the thorax over the fullest part of the bare breasts) and chest circumference (measured with a flexible tape horizontally placed around the thorax in the inframammary fold) (4). Maximal breast hemi-circumference (measured with a flexible tape crossing horizontally over the nipple) (9) and areolar diameter will be measured. Investigator will note Tanner stage of breast (5). Patients will be asked about feeling of fullness in breast (none, same as baseline, more than baseline) and their bra cup size.

*Testicular exam:* Both testes will be palpated while the subject is standing. Size of each testis will be compared against a standard orchidometer.

*Hirsutism/hair growth:* The degree of androgenic hair growth will be assessed by investigators according to the modified Ferriman and Gallwey (FG) scoring system (16, 17). Any shaving, depilation or waxing by the patient will be considered in the assessment. Shaving frequency will be recorded as times per week. Patients will be asked to rate their scalp hair growth (no change, better than before, worse than before) and scalp hair quality (no change, finer than before, coarser than before).

*Mood:* Subjects will complete two psychometric tests (18):-

- a) Body-image concern questions of Body-uneasiness test (BUT-BIC)(19): This questionnaire has 9 questions and is meant to capture worries related to physical appearance. Responses are recorded on a 6 point Likert scale. The mean of all 9 questions is presented as the global severity index.

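### Exclusion 3 covers only planned breast surgery, so people with existing augmentation can be randomised and no rule handles them in the secondary breast analyses

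*Combined protocol and SAP*

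**What the plan says.** All references are to the combined protocol and SAP.

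- **Exclusion Criteria, item 3**, the only surgical criterion: "Planning to go for breast enhancement or gender reassignment surgery in the next 6 months".
- **Exclusion Criteria, item 8**, the only other breast criterion: "Known, suspected, or history of breast cancer".
- **Inclusion criteria, item 1**: "Transwomen, currently on treatment with estradiol therapy for at least 6 months". There is a minimum duration but no maximum, and item 3 allows ages 18 to 65.
- **Background**: "at least 60% of transgender women seek surgical breast augmentation".
- **Study Procedures, Breast size**: "The primary measure of breast size will be the difference between breast circumference" and chest circumference at the inframammary fold. Hemi-circumference and areolar diameter are also measured. In addition, "Investigator will note Tanner stage of breast" and "Patients will be asked about feeling of fullness in breast (none, same as baseline, more than baseline) and their bra cup size".
- **Statistical analysis**: the primary endpoint is the 24-week change in total testosterone, and the sample size is set on it. The breast measures are listed under Secondary end-points and are analysed as change.

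None of the 3 inclusion or 11 exclusion criteria mentions completed augmentation. No visit calls for a record of prior breast surgery, and the statistical section has no rule for participants who have had it.

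**The concern.** Item 3 keeps out people whose breasts would be altered surgically during the 24 weeks. A person whose augmentation was completed before screening raises a closely related measurement problem, yet meets every criterion. Nor can exclusion of past surgery be read into the item. Where the protocol means to cover past conditions it says so (items 5 to 8, 10 and 11 all refer to history), and item 3 does not.

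None of the listed size measures separates an implant from native tissue. Tanner stage and bra cup size are the most exposed: both are coarse categories, and after augmentation the category may be set largely by the surgery.

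Breast development is in the trial's title, and an increase in breast size is part of its hypothesis. The background describes the question as still open for want of well-designed studies. A null breast result that included people unable to show a response would be harder to read.

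**Working it through.** **1. Check of the criteria.** This is a reading check, and it settles the gap itself. Item 3 is prospective, item 8 concerns cancer, and no other criterion touches the breast. The week 0 and week 24 breast exams would probably reveal implants, but nothing says what to do with that information.

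**2. The plan's own sample size.** Inputs from Statistical analysis: 20 per group, 15% dropout, power 0.80 (written there as β = 0.8), α = 0.05, and an SD no larger than the mean difference, so d = 1.0 at the limit. A two-sided test is assumed because sidedness is not stated.

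- Normal approximation: n = 2(1.96 + 0.842)² / 1² = 15.7, so 16 per group; 16 / 0.85 = 18.8, so 19.
- Exact two-sample t-test: n = 16.7, so 17 per group; 17 / 0.85 = 20.

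The stated 20 per group reproduces, and 20 × 0.85 = 17 completers per arm. This figure is not in dispute and does not depend on implants.

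**3. Why the tape measures are hit less.** Suppose a stable implant adds roughly c to the circumference difference at both visits. The change is (B₂₄ + c) − (B₀ + c) = B₂₄ − B₀. The addition is only approximate on a curved surface, so c largely rather than exactly cancels. Native growth could still register. A category such as Tanner stage or cup size has no such cancellation.

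**4. Illustration for a breast endpoint.** The documents give no share f with completed augmentation and no breast effect size or SD. Assumptions, none from the documents:

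- f runs from 5% to 20%, equal in both arms (0.05 × 40 = 2 to 0.20 × 40 = 8 of those enrolled);
- the true effect in people without augmentation is 1 SD, borrowed from the testosterone condition;
- carriers show no measurable response, and the SD is unchanged.

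Power is from the two-sided t-test with noncentrality d√(n/2) and 2(n − 1) degrees of freedom.

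- Carriers kept: d = 1 − f, n = 17.
- Carriers left out of the breast analysis: d = 1, n = 17(1 − f).
- Carriers excluded at entry and replaced: d = 1, n = 17.

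| f | Kept: d | Kept: power | Left out: n per arm | Left out: power | Replaced: power |
|---|---|---|---|---|---|
| 0% | 1.00 | 80.7% | 17 | 80.7% | 80.7% |
| 5% | 0.95 | 76.6% | 16.15 | 78.5% | 80.7% |
| 10% | 0.90 | 72.1% | 15.3 | 76.2% | 80.7% |
| 20% | 0.80 | 61.9% | 13.6 | 70.8% | 80.7% |

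Leaving carriers out gains 78.5 − 76.6 = 1.9 points at 5% and 70.8 − 61.9 = 8.9 points at 20%. Exclusion with replacement gains 80.7 − 76.6 = 4.1 and 80.7 − 61.9 = 18.8 points.

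**The case against.** The case against making much of this is substantial, and most of it stands as a limit on size.

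- **The endpoints are secondary.** Implants do not affect the testosterone analysis, and the plan makes no power claim for breast size. This stands.
- **Change cancels a fixed implant.** A reader might infer that all the breast measures would mainly describe the implant. For the change in circumference difference, which the protocol names as its main breast measure, and for hemi-circumference, that goes too far. Zero response in carriers is therefore a worst case for these measures.
- **Prevalence is unknown.** A reader might take the background's 60% as the share with implants, or conclude that carriers must be common in the clinic. The figure is the share who seek surgery. It is neither the share who have had it nor the share of those who would then join this trial. The absence of an upper limit on estradiol duration makes such entrants possible, not frequent; the number could be zero.
- **Direction.** Allocation is randomised 1:1 and double-blind, so no systematic bias in favour of either arm is expected. What remains is dilution, noise and the possibility of chance imbalance with few participants.
- **Drift after recent surgery.** A reader might suppose that a new implant changes shape over the 24 weeks. Nothing in the documents supports this, and the point does not rely on it.
- **Implants would probably be noticed at the breast exams.** This is a partial safeguard: it makes carriers identifiable. Without a prespecified rule, though, the decision to keep or drop them would be made during or after the trial.

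None of this closes the gap in eligibility and analysis.

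**Conclusion.** The concern holds as a modest, cheaply corrected gap confined to the secondary breast endpoints. The plan admits people with completed augmentation and says nothing about their breast data. That part rests on the text alone and is firm. Interpretation is weakest for Tanner stage and bra cup size.

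The size of the effect is uncertain. Under the stated assumptions, a 1 SD breast effect would be detected with 77% power at 5% carriers and 62% at 20%, against 81% with none. It would be wrong to quote the fall to 62% alone as the expected loss: it combines the top of an assumed range, a borrowed effect size and zero response in carriers. Nor do the documents support a reading in which the trial's main result is compromised.

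**What to change.** Either of two changes is enough.

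1. **Exclude at entry.** Extend exclusion 3 to prior breast augmentation (implant or fat transfer) as well as planned surgery. The cost is one clause and a slightly smaller eligible pool. Under the assumed 5% to 20%, reaching 40 would take 40 / 0.95 = 42.1 (43) to 40 / 0.80 = 50 otherwise eligible people.
2. **Record and set aside.** Add a screening question on prior breast surgery, and prespecify that participants with augmentation are left out of all breast endpoints in both arms while staying in the testosterone analysis. Because the status is fixed before randomisation, leaving them out does not undermine the comparison. The cost is a slightly smaller breast analysis: under the same assumption, about 34 × 0.95 = 32 to 34 × 0.80 = 27 of the 34 expected completers.

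The first keeps full power for the breast endpoints; the second keeps recruitment unchanged. Neither alters the planned 20 per group, which is set on testosterone.

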### **Study Procedures**

*Clinical laboratory assays:* All measurements will be carried out by Quest diagnostics as part of a standardized contract. We have previously published studies in which measurements of testosterone and estradiol on serum samples of our study subjects were done by Quest Diagnostics (12, 13). Testosterone and estradiol will be measured by current “gold standard” assay: liquid chromatography tandem mass spectrometry. SHBG, FSH and LH concentrations will be measured by a solid-phase, chemiluminescent immunometric assay (Siemens, IMMULITE 2500). Free testosterone and estradiol will be calculated using concentrations of total testosterone, total estradiol, SHBG and albumin by the formula of Sodergard *et al* and Vermuelen *et al* (14, 15).

*Breast size:* The primary measure of breast size will be the difference between breast circumference (measured in centimeters with a tape placed horizontally around the thorax over the fullest part of the bare breasts) and chest circumference (measured with a flexible tape horizontally placed around the thorax in the inframammary fold) (4). Maximal breast hemi-circumference (measured with a flexible tape crossing horizontally over the nipple) (9) and areolar diameter will be measured. Investigator will note Tanner stage of breast (5). Patients will be asked about feeling of fullness in breast (none, same as baseline, more than baseline) and their bra cup size.

*Testicular exam:* Both testes will be palpated while the subject is standing. Size of each testis will be compared against a standard orchidometer.

*Hirsutism/hair growth:* The degree of androgenic hair growth will be assessed by investigators according to the modified Ferriman and Gallwey (FG) scoring system (16, 17). Any shaving, depilation or waxing by the patient will be considered in the assessment. Shaving frequency will be recorded as times per week. Patients will be asked to rate their scalp hair growth (no change, better than before, worse than before) and scalp hair quality (no change, finer than before, coarser than before).

*Mood:* Subjects will complete two psychometric tests (18):-

- a) Body-image concern questions of Body-uneasiness test (BUT-BIC)(19): This questionnaire has 9 questions and is meant to capture worries related to physical appearance. Responses are recorded on a 6 point Likert scale. The mean of all 9 questions is presented as the global severity index.
- b) Symptom-Checklist-K-9 (SCL-K-9) to measure psychological distress level(20): This questionnaire has 9 questions and is meant to assess overall psychological distress. Responses are recorded on a 5 point Likert scale. The mean of all 9 questions is presented as the global severity index.

*Sleep quality:* We will use single-item sleep quality scale (SQS) to assess change in sleep quality during the study.

FG score calculator and study questionnaires are attached in the IRB application.

*Research labs:* 10 ml of blood will be obtained for research. Serum will be stored for future analysis based on study results. For example, if there is a decrease in FG score, we will check dihydrotestosterone levels.

**Side effects:** Progesterone may cause fluid retention, mood swings, breast tenderness, depression, transient dizziness and drowsiness, headache, abdominal pain or bloating, hot flashes in women. Long term use is associated with possibly increased risk of heart disease and stroke in women after menopause. Short term and long term risks in transwomen are not known.

If a significant or serious adverse event occurs, the subject will cease participation in the study. Discovery of two or more patients experiencing a significant or serious adverse event will lead to stopping of this study altogether.

**Statistical analysis:** The primary end-point of the study is change in total testosterone concentrations in transwomen after progesterone treatment at 24 weeks as compared to placebo. Transformations of the

data to meet statistical assumptions may be considered. *t*-test will be used for comparison. We estimate that testosterone concentrations will decrease by 20%. A sample size of 20 subjects per group (assuming a drop-out rate of 15%) will provide adequate power ( $\beta = 0.8$ ) to detect a significant difference ( $\alpha = 0.05$ ), provided the pooled standard deviation is not greater than the mean difference. Hence, we will recruit 40 transwomen in this study.

*Secondary end-points:* Change at weeks 12 and 24 in a) LH and FSH concentrations, b) breast size, breast hemi-circumference, areolar diameter, Tanner stage, feeling of fullness in breast, bra cup size, c) FG score, shaving frequency, scalp hair growth, scalp hair quality, d) global severity index scores on BUT-BIC and SCL-K-9 scales, e) SQS score.

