There are transgender females who report an anecdotal improved breast development, mood, or sleep with the use of progestogens(7). Estrogen is important for stromal and early ductal and epithelial proliferation(2). By contrast, although progesterone in cell culture causes proliferation for a few days, it then transforms into its primary, maturational role that includes inhibition of the proliferative effects of E2 (7, 8). Progesterone appears to be relevant for acini/lobuli development and pseudolactational changes. Many women report a feeling of fullness in breasts and their transformation from a conical to more rounded shape (clinical experience of PI). Thus, progesterone may induce optimal breast maturation, if preceded by estradiol therapy in transwomen. However, observational studies with small number of patients do not support a major role for progesterone in enhancing breast size in transwomen (9). There have been no well-designed studies of the role of progestogens in feminizing hormone regimens, so the question is still open. As per Endocrine society transgender guidelines, “current evidence does not indicate that progestogens enhance breast development in transgender females, nor does evidence prove the absence of such an effect. This prevents us from drawing any firm conclusion at this moment and demonstrates the need for further research” (1).

Progesterone has a minor suppressive effect on GnRH production, and this would decrease endogenous testosterone production. In a chart review, transwomen using medroxyprogesterone (in combination with estradiol and spironolactone) had lower testosterone concentrations than those on estradiol and spironolactone alone (79 vs 215 ng/dl)(10). Progesterone also competes for the 5- $\alpha$  reductase enzyme that converts T into dihydrotestosterone (11). These effects would theoretically be desirable in the feminization of transwomen.

We plan to conduct a randomized, placebo controlled double blind study evaluating the effect of adding progesterone for 6 months to transwomen who are being treated with estradiol. We hypothesize

that progesterone will decrease serum testosterone concentrations as compared to placebo and increase breast size. We will also assess its role in mood, sleep, scalp hair and androgenic hair growth.

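### As printed, the breast-fullness item has no answer for fullness that fell without disappearing, and its 'none' option is undefined (minor)

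*Combined protocol and SAP*

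**What the plan says.** Under Study Procedures, Breast size, the combined protocol and SAP sets out the item: "Patients will be asked about feeling of fullness in breast (none, same as baseline, more than baseline) and their bra cup size". The Secondary end-points paragraph uses it as a change measure: "Change at weeks 12 and 24 in a) LH and FSH concentrations, b) breast size, breast hemi-circumference, areolar diameter, Tanner stage, feeling of fullness".

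The Hirsutism/hair growth paragraph builds its patient-rated items differently: "Patients will be asked to rate their scalp hair growth (no change, better than before, worse than before". The scalp hair quality item that follows also offers no change and both directions.

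The document does not define 'none', rank the three fullness answers, say which takes precedence when two apply, or describe how the item is put at week 0. It does say where the forms are: "FG score calculator and study questionnaires are attached in the IRB application".

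**The concern.** 'None' describes a level at the time of asking. 'Same as baseline' and 'more than baseline' describe a comparison. A single list that mixes the two need not cover every participant, nor give each exactly one answer. Here the upper end is clear and the lower end is not.

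What is at stake is the recording of decreases on one named secondary end-point. The hypothesis is directional, "that progesterone will decrease serum testosterone concentrations as compared to placebo and increase breast size", but the planned analysis is a two-arm comparison of change, and the background calls the role of progestogens an open question. A participant with a partial decrease must pick an answer that is untrue or leave the item blank. A tick at 'none' could stand for no change or for complete loss.

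**Working it through.** The plan gives no figure for this item, so the check is logical. The stated 20 per group belongs to the primary testosterone endpoint and does not enter.

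**Inputs**
- The three printed answers (Study Procedures, Breast size).
- Use as change at weeks 12 and 24 (Secondary end-points).
- Assumption, for illustration only: fullness graded 0 to 3, with 0 meaning absent. The document gives no such scale.

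**Literal rule.** With baseline grade b and follow-up grade f, 'none' is true if f = 0, 'same' if f = b and 'more' if f > b. There are 4 × 4 = 16 pairs.

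| Pairs (b to f) | Number | Answers that are true |
|---|---|---|
| 0 to 0 | 1 | 'none' and 'same' |
| 1 to 1, 2 to 2, 3 to 3 | 3 | 'same' only |
| all with f > b | 6 | 'more' only |
| 1 to 0, 2 to 0, 3 to 0 | 3 | 'none' only |
| 2 to 1, 3 to 1, 3 to 2 | 3 | no answer |

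The total is 1 + 3 + 6 + 3 + 3 = 16. Exactly one answer fits in 3 + 6 + 3 = 12 pairs. The 3 pairs without an answer are all partial decreases, and the one pair with two answers is the person who never had fullness. These are counts of logical possibilities, not expected proportions of participants.

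**Dependence on the scale.** With top grade k, the pairs without an answer number k(k − 1)/2, which is 0, 1 and 3 for k = 1, 2 and 3. There is one overlap whatever k is. So the gap exists once fullness has two or more non-zero grades, which 'more than baseline' already presupposes for anyone who has fullness at the start.

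**Other readings of 'none'**
- *No fullness now, taking precedence over 'same'.* The split is 'none' 4, 'same' 3, 'more' 6, no answer 3 (total 16). The overlap goes and the gap stays. 'None' then holds one unchanged pair and three complete losses, which only a week 0 answer can separate.
- *No increase.* 'None' then covers all 16 − 6 = 10 pairs with f ≤ b: 4 unchanged and 6 decreases. It overlaps 'same' in the 4 unchanged pairs, and no decrease of any size can be identified.

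**The revised item, same check.** Less/same/more gives 6 + 4 + 6 = 16, one answer per pair. A yes/no question on presence now divides the 6 decreases into 3 partial (present) and 3 complete (absent). Asked at week 0 as well, it identifies those who never had fullness ('same', absent at both times).

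**What survives under the printed item.** Under the literal rule 'more' is true in the 6 pairs with f > b and in no other, so the proportion answering 'more than baseline' can be compared between arms. One caution: a partial decrease left blank cannot be told from any other blank and may drop out of the denominator.

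**The case against.** The strongest objection is that the printed parenthesis is a one-line summary and the instrument itself is in the IRB application. This stands. A reader might infer that the trial is collecting faulty data; the document shows only a fault in the printed wording, and the effect on the data depends on the form matching it.

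Second, the overlap can be read away. If 'none' means no fullness now and a week 0 answer exists, never-present and lost can be separated. Questionnaires are completed at week 0, but the document does not say this item is among them, and two of its three answers refer to a baseline that is only then being set. So the second fault is conditional. The missing answer for a partial decrease survives this reading.

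Third, a reader might infer from the background that a decrease in fullness is expected, because of progesterone "it then transforms into its primary, maturational role that includes inhibition of the proliferative effects of E2". The document does not support that. The sentence concerns proliferation, in the context of cell culture, not perceived fullness. The background's one remark on fullness, from the principal investigator's clinical experience, points to an increase, which the item can record. The case for a downward answer rests on the two-arm comparison of change and on the hair items, not on a predicted decrease.

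Fourth, a reader might infer a loss of power. The document gives no response rates for this item and names no test for it, so any power figure would rest on assumptions, and for an increase the result can go either way according to the decreases assumed in each arm.

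**Conclusion.** The point holds as a minor fault in a stated response set. As printed, partial decreases have no answer, and 'none' needs a definition, a precedence rule and a week 0 answer before it can be read one way. This follows from the wording alone and needs no assumed response rates. It rests on one assumption: that the form in the IRB application uses the same three answers.

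The reach is narrow. It affects the lower end of one patient-reported item among many secondary end-points. 'More than baseline' remains interpretable, and the primary endpoint and sample size do not change.

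One reassurance should not be drawn. A reader might assume that the measured breast dimensions would show a decrease at week 12 anyway. The visit descriptions list a breast exam at weeks 0 and 24 but not at week 12, so the document supports that assumption only for week 24.

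**What to change.** 1. Compare the protocol text with the questionnaire in the IRB application. If the form already has suitable answers, correct the protocol line to match. Cost: one line of text.
2. If the form carries the printed answers, ask at weeks 12 and 24 whether fullness is less than, the same as or more than at baseline. Add a yes/no question on whether fullness is present now, at weeks 0, 12 and 24. The presence question is needed at all three visits: asked only at week 0, it would merge partial with complete loss, and complete loss is something the present 'none' can record.
3. Compare the rating itself between arms at each visit. It is already relative to baseline, so no change score should be computed from it. 'More' against not 'more' remains available.
4. If the old item has to stay, compare the proportion answering 'more than baseline', and state how blanks at attended visits are counted.

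Cost of steps 2 and 3: one edited item with a short added question, and a minor IRB amendment. Answers already collected cannot be fully mapped. Old 'more' carries over; old 'same' may hide partial decreases, and old 'none' may be either no change or complete loss.
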